9.4.4 Exploratory Endpoint 4: Self-reported acceptability and adherence to vaginal ring use

Consistent with exploratory objective 4, exploratory endpoints 4 and 5 are the proportion of participants who respond positively to questions on ring acceptability at the last product use visit, and participant self-reported patterns of ring use, respectively.

Assessments – Self-reported acceptability

Participant questionnaires will be administered at every trial visit after enrollment, until the last product use visit.

Statistical methods – Self-reported acceptability

The proportion of participants among all trial participants who respond positively (i.e. Yes) to the following two questions at the last product use visit:

- “Do you think it is possible for women to use the ring as requested (i.e. without removing it)?”
- “Do you think women in your community would want to use this ring if it were available?”

A participant will be classified as having found the vaginal ring acceptable if she responds positively to the first question, about keeping the ring inserted as prescribed. Community acceptability will be demonstrated by positive responses to the second question. For each question, the proportion of participants who responded positively,

and the corresponding Fisher's exact 95% confidence interval, will be calculated and presented.

Summary tables with descriptive statistics will be presented for the socio-demographic variables and psycho-social variables collected in the participant questionnaires.

Note: Additional explanatory analyses will utilise the qualitative data from focus group discussions and individual interviews; these analyses will be performed separately from the analyses described in this analysis plan, and will be discussed in the Clinical Study Report.

Assessments – Self-reported adherence

Information on rings dispensed and returned are recorded at each trial visit on the RL CRF. Participant self-reports of accidental ring expulsions and removals are recorded on the EXP CRF.

Statistical methods – Self-reported adherence

Self-reported adherence to the ring regimen will be calculated per visit, and presented descriptively overall and by research centre. The adherence rate per visit will be calculated as:

- $100 \times (\text{number of days that the participant reportedly wore the ring} / \text{the total number of days that the participant was expected to wear the ring})$.

The number of days that the participant reportedly wore the ring is based on data captured in the Ring Insertion/Removal Log (RL) CRF and the EXP CRF at the scheduled visit and any preceding unscheduled visit between the current and the previous scheduled visit. The total number of days that the participant was expected to wear the ring is a calendar month (30 days) from the insertion date.

The self-reported adherence rates will be presented in the following categories:

- $\geq 90\%$
- $\geq 80\% \text{ to } < 90\%$
- $< 80\%$.

Summary tables with descriptive statistics will be presented for accidental ring expulsions and removals by the participant for reasons other than instructed by the research centre staff.

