2.4 Assessment of Objectives

Consistent with the primary objectives, the **primary endpoints** are:

Safety

- All Adverse Events (AEs) assessed by the investigator to be related to the Dapivirine Vaginal Ring-004.

- All Grade 3 and 4 AEs.
- All Serious Adverse Events (SAEs).

Adherence

Residual amounts of dapivirine in returned rings and/or dapivirine concentrations in plasma and/or dapivirine concentrations in vaginal fluid.

The primary endpoints will be assessed through:

Safety

All product-related AEs, Grade 3 or 4 AEs, SAEs, physical examination, gynaecological assessments, including pelvic/speculum examination, laboratory tests and other indicated investigations.

Adherence

- Determined dapivirine residual amounts in returned used vaginal rings and/or
- Measured concentrations of dapivirine in plasma [**Not implemented**] and/or
- Measured concentrations of dapivirine in vaginal fluids [**Not implemented**.]

Consistent with the secondary objectives, the **secondary endpoints** are:

- The HIV-1 seroconversion rate per 100 woman-years of product use at the end of the vaginal ring use period.
- HIV-1 drug resistance mutations among participants who acquire HIV-1 infection.

The secondary endpoints will be assessed through:

- Rapid and specialised laboratory testing according to a pre-specified HIV testing algorithm.
- Viral genotype resistance testing methods which include sensitive methods to detect low frequency drug-resistant variants (only population genotyping will be done.)

Consistent with the exploratory objectives, the **exploratory endpoints** include:

- Feasibility of a 3-monthly clinical follow-up schedule.
- Dapivirine residual amounts in returned used vaginal rings and/or dapivirine concentrations in plasma and/or vaginal fluid in correlation with results from the visual inspection of the returned used vaginal rings by research staff.
- Proportion of participants opting for HIV rapid tests at the research centre between scheduled 3-monthly research centre follow-up visits.
- The proportion of women who report the use of the vaginal ring as acceptable.
- Participant self-reported patterns of ring use.

The exploratory endpoints will be assessed through:

- Participant report of feasibility regarding a 3-monthly clinical follow-up schedule (Participant Questionnaire).
- Number of women opting not to receive two additional rings at the 3-monthly visits.

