5.1 Safety Population

The safety population will include all participants who were enrolled, and received and inserted at least one Dapivirine Vaginal Ring

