Safety Population

LPUV Question	Statistic	IPM 032 Overall (N=XXX)
Participants who responded positively to the following Do you think it is possible for women to use the ring as requested (i.e. without removing it)?	n (%) ^a 95% CI ^b	X (X.X) XX, XX
Do you think women in your community would want to use this ring if it were available?	n (%) ^a 95% CI ^b	X (X.X) XX, XX

CI = Confidence interval; LPUV = Last product use visit

^a Percentages are calculated out of the number of participants in the safety population

^b 95% CI calculated using Fisher's exact test

A participant will be classified as having found the vaginal ring acceptable if she responds positively to the first question, about keeping the ring inserted as prescribed. Community acceptability will be demonstrated by positive responses to the second question

Table 14.3.5.7
 Accidental Ring Expulsion/ Removal
 Safety Population

Visit	Reason Ring Was Removed / Came Out	Statistic	IPM 032 Overall (N=XXX)
Trial Month X	Participants who had an accidental ring removal/expulsion	n (%) ^a	X (X.X)
	Participants who had no accidental ring removals/expulsions	n (%) ^a	X (X.X)
...			

^a Percentages are calculated out of the number of participants in the safety population

Table 14.3.6.1
Vital Signs
Safety Population

Parameter (unit) Visit	Statistic	Centre 01				All Centres		
		IPM 027 Dapivirine (N=XXX)	IPM 027 Placebo (N=XXX)	IPM 032 Overall (N=XXX)	...	IPM 027 Dapivirine (N=XXX)	IPM 027 Placebo (N=XXX)	IPM 032 Overall (N=XXX)
Parameter (unit)								
Baseline	n	XXX	XXX	XXX	...	XXX	XXX	XXX
	Mean	XX.X	XX.X	XX.X	...	XX.X	XX.X	XX.X
	(q1,med,q3)	(XX.X,XX.X,X X.X)	(XX.X,XX.X,X X.X)	(XX.X,XX.X,X X.X)	...	(XX.X,XX.X,X X.X)	(XX.X,XX.X,X X.X)	(XX.X,XX.X,X X.X)
	SD	XX.XX	XX.XX	XX.XX	...	XX.XX	XX.XX	XX.XX
	(Min, Max)	(XX, XX)	(XX, XX)	(XX, XX)	...	(XX, XX)	(XX, XX)	(XX, XX)
LPUV	n	XXX	XXX	XXX	...	XXX	XXX	XXX
	Mean	XX.X	XX.X	XX.X	...	XX.X	XX.X	XX.X
	(q1,med,q3)	(XX.X,XX.X,X X.X)	(XX.X,XX.X,X X.X)	(XX.X,XX.X,X X.X)	...	(XX.X,XX.X,X X.X)	(XX.X,XX.X,X X.X)	(XX.X,XX.X,X X.X)
	SD	XX.XX	XX.XX	XX.XX	...	XX.XX	XX.XX	XX.XX
	(Min, Max)	(XX, XX)	(XX, XX)	(XX, XX)	...	(XX, XX)	(XX, XX)	(XX, XX)
Change from baseline to LPUV	n	XXX	XXX	XXX	...	XXX	XXX	XXX
	Mean	XX.X	XX.X	XX.X	...	XX.X	XX.X	XX.X
	(q1,med,q3)	(XX.X,XX.X,X X.X)	(XX.X,XX.X,X X.X)	(XX.X,XX.X,X X.X)	...	(XX.X,XX.X,X X.X)	(XX.X,XX.X,X X.X)	(XX.X,XX.X,X X.X)
	SD	XX.XX	XX.XX	XX.XX	...	XX.XX	XX.XX	XX.XX

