37 It may be hard for women to use the ring all the time without taking it out. Do you think it is possible for women to use the ring as requested (i.e. without removing it)?

38 What do you think are the most likely reason(s) for a woman to take out her ring?

39 Please say whether you strongly agree, agree somewhat or disagree with the following statements below:

39a All women can use the ring without taking it out.

39b Women would need a break from using the ring every few months.

40 Do you think women in your community would want to use this ring if it were available?

41 If the ring is made available to the public, where do you think most women would want to get it from?

42 If the ring is made available to the public, how much would you be prepared to pay for it?

43 If the ring is made available to the public, where do you think it should be marketed/advertised?

Listing 16.2.5.10
 Participant Questionnaire – Last Product Use Visit
 Safety Population

Centre Participant ID	Visit Date	Visit	Q1	Q1a	Q2
Centre XX XXXXXXXX	ddMMMyyyy	Screening / Enrollment / Trial Month XX / Trial Month XX (Unscheduled X) / Exit visit	Always took it / Always left it at the centre to collect monthly / Sometimes took it sometimes left it at the centre / Chose not to answer	Initially leave it at the centre then later start taking it / Initially take it then start leaving it at the centre / It varied: XXXXXXXXXXXXXXX / Chose not to answer	Did not want anyone to see the rings / Did not have a private place to keep the unused rings / Did not have a private place to keep the used rings / Did not have an appropriate storage place to keep the rings / Did not have a private place to insert the rings / Worried I might lose the ring(s) / Felt I might forget to insert the new ring if I didn't come each month / Liked coming to the centre for HIV tests each month / Liked coming to the research centre monthly for social reasons / Other: XXXXXXXX / Chose not to answer

Programmers Note: Please capture multiple responses, separated with a ‘;’

LPUV = Last product use visit

Rank: 1 = Liked the most; 2 = Liked second most; 3 = Liked; 4 = Liked a little; 5 = Liked the least

Centre 01: Madibeng Centre for Research (MCR); Centre 02: MatCH Research Unit (MRU); Centre 04: Qhakaza Mbokodo (QM);

Centre 06: MRC/UVRI & LSHTM Uganda Research Unit (MRC/UVRI); Centre 07: Desmond Tutu HIV Foundation (DTHF), Masiphumelele; Centre 08: Ndlovu Care Group (NCG)

Listing 16.2.5.10

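### The acceptability percentage in SAP 9.4.4 measures perceived feasibility for women in general and, taken over the whole safety population, is an unlabelled lower bound

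*SAP*

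**What the plan says.** SAP 2.4 lists as an exploratory endpoint "The proportion of women who report the use of the vaginal ring as acceptable". SAP 9.4.4 makes this operational with two LPUV questions. The first is "Do you think it is possible for women to use the ring as requested (i.e. without removing it"; the second asks whether women in the participant's community would want the ring if it were available. The rule that follows is: "A participant will be classified as having found the vaginal ring acceptable if she responds positively to the first question". Table 14.3.5.6 repeats the rule in its footnote. In the LPUV questionnaire (Listing 16.2.5.10, question 37) the item is introduced by "It may be hard for women to use the ring all the time without taking it out".

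The statistic is "The proportion of participants among all trial participants who respond positively (i.e. Yes) to the following two questions at the last product use visit", with an exact 95% confidence interval. Footnote a of Table 14.3.5.6 fixes the denominator: "Percentages are calculated out of the number of participants in the safety population". Under SAP 5.1, "The safety population will include all participants who were enrolled, and received and inserted at least one Dapivirine Vaginal Ring", so membership does not depend on reaching the LPUV.

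Protocol 4.4 gives the questionnaire at the LPUV or early discontinuation visit. Protocol 4.9 encourages women who stop early to return for the LPUV procedures. If the LPUV is missed, Protocol 4.7 moves only STI testing to the Exit Visit, and Appendix A schedules no questionnaire there. Listing 16.2.5.2 allows Don't know and Chose not to answer for the first item. SAP 6.2 expects some missing data, mainly from missed visits, and gives no rate.

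**The concern.** There are two separate difficulties.

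The first is content. The endpoint is about what each woman reports of her own use; the deciding item is her opinion of what women in general can do. A woman who took out her own ring because it was uncomfortable can still answer Yes. A woman content with the ring who doubts that others could keep it in can answer No.

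The second is the denominator. A woman never asked cannot respond positively but stays in the denominator, so the figure moves with retention as well as opinion. Section 9.4.4 provides no respondent denominator, no missing row and no statement that the figure is a bound. The neighbouring analyses differ: Table 14.3.5.5 (self-reported adherence) restricts percentages to women with available data, and SAP 9.4.3 divides by women with at least one HIV rapid test. Nothing in 9.4.4 explains the difference.

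At stake is a percentage headed acceptability in the study report whose content is perceived feasibility and whose level depends partly on how many women returned.

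**Working it through.** The documents state no acceptability figure, so there is nothing to reproduce. The check is what the planned statistic equals.

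**Inputs**
- N = 1400, the anticipated sample size (SAP 3.2), standing in for the safety population.
- p, the proportion of Yes among women who answer: assumed 0.90, with 0.80 and 0.95 as a range.
- d, the share of N with no answer: assumed 0 to 20%.
- Interval: the exact 95% interval, computed as Clopper-Pearson.

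**Formula.** Let m be the number who answer and x the number who say Yes. The planned statistic is x/N = (x/m) × (m/N), the respondent proportion times the answering rate.

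**Results for p = 0.90**

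| No answer | Planned x/N (95% CI) | Respondents x/m (95% CI) | Missing all No to all Yes |
|---|---|---|---|
| 0% | 1260/1400 = 90.0% (88.3-91.5) | same | 90.0% |
| 5% | 1197/1400 = 85.5% (83.5-87.3) | 1197/1330 = 90.0% (88.3-91.6) | 85.5-90.5% |
| 10% | 1134/1400 = 81.0% (78.8-83.0) | 1134/1260 = 90.0% (88.2-91.6) | 81.0-91.0% |
| 20% | 1008/1400 = 72.0% (69.6-74.3) | 1008/1120 = 90.0% (88.1-91.7) | 72.0-92.0% |

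The last column is x/N to (x + N − m)/N; at 10% the upper end is (1134 + 140)/1400 = 91.0%. The planned figure is always the lower end of that range.

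**Sensitivity to p.** With 10% unanswered, the plan prints 1008/1400 = 72.0% when p = 0.80 and 1197/1400 = 85.5% when p = 0.95.

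**How little non-response is needed.** At p = 0.90, 26 unanswered of 1400 (1.9%) already put the upper limit of the printed interval below 90%. The corresponding numbers are 39 (2.8%) at p = 0.80 and 18 (1.3%) at p = 0.95. The interval carries only binomial sampling error on N and nothing for the unanswered.

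No arithmetic bears on the content difficulty. Setting SAP 2.4 beside question 37 and its lead-in is enough: the endpoint concerns the respondent's own report, the item concerns women.

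**The case against.** The strongest reply is that the plan hides little. Table 14.3.5.6 prints the full question as its row label, and 9.4.4 says the item is about keeping the ring inserted as prescribed. Table 14.6.9 tabulates the same item as Yes / No / Don't know, with a programmer's note to add a declined row where applicable, so the number without an answer follows by subtraction from N. A reader might infer that the figure cannot be interpreted at all; given that table, this goes too far.

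Acceptability does not rest on this item alone. The questionnaire tables also cover each woman's own removals and reasons, ease of insertion and removal, and willingness to pay. Focus groups and interviews are analysed separately and discussed in the study report.

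Three other stronger readings are not supported.
- A reader might infer that women without an answer are classed as finding the ring unacceptable. The SAP has no such category; they are only not counted as positive. A Don't know is properly not a Yes.
- A reader might infer that all early discontinuers go unasked. Those who return for the final evaluation receive the questionnaire.
- A reader might infer that every missing LPUV lowers the figure. Against complete data, only a missing would-be Yes does.

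It is also fair that the all-participants figure is the conservative one. SAP 6.2 warns that missing-data patterns may be informative for adherence; if dissatisfied women leave, the respondent figure errs upward.

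What stands is that neither the classification sentence nor the table title describes what the item measures, and that the headline percentage is a bound not presented as one.

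**Conclusion.** The point holds in a limited form. As planned, the acceptability percentage is perceived feasibility for women in general, expressed as the respondent proportion times the answering rate. It is a missing-equals-not-Yes lower bound, unlabelled, with an interval that ignores non-response. Under the assumed 90% Yes and 10% unanswered of 1400, the gap from the respondent figure is 9 percentage points (81.0% against 90.0%). These rates are assumptions, and the size scales with them.

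The documents do not show that the respondent figure is the true one. Reading the gap as bias of that size requires women without an answer to resemble those who answered. The endpoint is exploratory and descriptive, with no hypothesis attached, so this is a matter of labelling and presentation. It is a minor point, but cheap to put right.

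**What to change.** In SAP 9.4.4 and Table 14.3.5.6:
- Label the first item by its content: thinks use as requested is possible for women.
- Replace the classification sentence, in the text and the table footnote, with a statement that the item is an indirect indicator of acceptability, read alongside the participant's own removal reasons and the qualitative data. Deleting the sentence without a replacement would leave the SAP 2.4 endpoint with no stated quantitative analysis.
- Report the proportion and exact interval among women who answered, with counts for Yes, No, Don't know, declined and no LPUV. State whether Don't know counts as an answer; keeping it in the denominator is the natural choice.
- Give the all-participants figure beside it, labelled as a lower bound.
- Apply the same denominators to the second item, and align the endpoint wording in SAP 2.4.

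No new data are needed; the cost is wording and a few table rows. The trial would claim less on acceptability. The respondent figure may err upward if dissatisfied women leave, which is why both figures should be shown.

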5.13. Vaginal Ring Dispensing

Vaginal rings will be dispensed at the Enrolment Visit and subsequent Trial Visits. In the event that a participant will be away and unable to attend one of the Trial Visits where new vaginal ring(s) would be dispensed, the investigator or designee could dispense additional ring(s) on a case-by-case basis. All such circumstances must be documented fully by the investigator as described in the IPM 032 SOM. If a participant requires an additional ring at a time other than when they are scheduled to receive one, they will be required to attend the clinic for an interim visit. During the monthly trial visit period, the participants will be instructed to self-insert the newly-dispensed vaginal ring at the research centre and to remove the ring at the next scheduled visit. During the 3-monthly trial visit period, the participants should self-insert one ring during the trial visit and each of the two additional rings at monthly intervals until their next scheduled research centre visit. Vaginal ring bags will be provided to participants during the 3-monthly trial visit period for the storage of the used rings, together with instructions on the storage of the unused and used rings.

During the 3-monthly trial visit period, optional vaginal ring dispensing and return arrangement will be made with participants who prefer not to have additional vaginal rings in their possession. These participants will be provided with the option to return used vaginal rings and to collect new rings at the research centres at time intervals suitable to them, provided that the intervals allow for new vaginal rings to be inserted monthly. Optional HIV rapid tests will be offered to participants during these interim visits and will be conducted according to the Trial Visits HIV algorithm (refer to Appendix B). Participants' preference regarding the intervals for product dispensing and return will be documented in the source document and applicable CRFs.

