In instances where the date of IP initiation, *i.e.* the start date of ring use, is missing or unknown, the missing date will be imputed with the date of the enrollment visit.

In accordance with the protocol, each scheduled visit has a window period of \pm 7 days. If the participant does not return to the research centre for a scheduled visit prior to the start of the trial window of the next visit, the visit will be considered missed. If a participant presents for a visit outside the window for a scheduled trial visit, but prior to the start of the window for the next visit, it will be treated as a late visit. Missed visits and late visits will be documented as protocol deviations (refer to Section 7.2). Data recorded at late visits will be analysed as pertaining to the scheduled visit. Unscheduled visits may be performed at any time during the trial. If an unscheduled visit takes place within any given window period and any repeat observations are made within the given window period, the repeat values will be captured as pertaining to the unscheduled visit. Data from scheduled and unscheduled visits will be shown in the participant listings, and listings will be appropriately labelled when data arise from unscheduled visits. Data from scheduled visits will be presented in the summary tables.

Visit Schedule A will consist of participants who attend Trial Month Visits 1, 4, 7, 10, 13, and 16/Exit; Visit Schedule B will consist of participants who attend Trial Month Visits 1, 2, 5, 8, 11, 14, and 17/Exit; and Visit Schedule C will consist of participants who attend Trial Month Visits 1, 2, 3, 6, 9, 12, and 15/Exit.

Tables, figures, and listings of trial results will accompany the text of the CSR. Listings of all clinical data recorded in the CRFs will be provided, except for those CRFs which are used for administrative purposes, such as the Participant Encounter Form (PEN) and the End of Trial Inventory (ETI). Listings will be sorted by research centre and participant identification number (PID), and key variables such as visit date and/or trial visit number will be presented in each listing.

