Centre 01: Madibeng Centre for Research (MCR); Centre 02: MatCH Research Unit (MRU); Centre 04: Qhakaza Mbokodo (QM);
Centre 06: MRC/UVRI & LSHTM Uganda Research Unit (MRC/UVRI); Centre 07: Desmond Tutu HIV Foundation (DTHF), Masiphumelele; Centre 08: Ndlovu Care Group (NCG)

Listing 16.2.5.4
Ring Insertion/ Removal
Safety Population

Centre Participant ID	Month To Be Used In	Batch No.	Dispensed			Insertion		
			Replacement Ring	Visit Dispensed	Dispensed Date	Inserted Ring	Insertion Date	Re- Educated?
Centre XX XXXXXXXXX	XX	XXXXXX	Yes / No	Screening / Enrollment / Trial Month XX / Trial Month XX (Unscheduled X) / Exit visit	ddMMMyyyy	Yes / No: XXXXXXXXXXXX	ddMMMyyyy	Yes / No

Duration of Ring Use = (Removal Date – Inserted Date)+1

Centre 01: Madibeng Centre for Research (MCR); Centre 02: MatCH Research Unit (MRU); Centre 04: Qhakaza Mbokodo (QM);
Centre 06: MRC/UVRI & LSHTM Uganda Research Unit (MRC/UVRI); Centre 07: Desmond Tutu HIV Foundation (DTHF), Masiphumelele; Centre 08: Ndlovu Care Group (NCG)

Listing 16.2.5.4
Ring Insertion/ Removal
Safety Population

Centre Participant ID	Removal Date	Duration of Ring Use (Days)	Required Assistance with Removal	Re- Educated?	Removal	
					Ring Returned to Research Centre	Reason Not Returned to Research Centre
Centre XX XXXXXXXXX	ddMMMyyyy	XX	Yes / No	Yes / No	Yes / No	Lost ring / Flushed down toilet / Forgot ring / Discarded ring / Other: XXXXXXXX

Duration of Ring Use = (Removal Date – Inserted Date)+1

Centre 01: Madibeng Centre for Research (MCR); Centre 02: MatCH Research Unit (MRU); Centre 04: Qhakaza Mbokodo (QM);
Centre 06: MRC/UVRI & LSHTM Uganda Research Unit (MRC/UVRI); Centre 07: Desmond Tutu HIV Foundation (DTHF), Masiphumelele; Centre 08: Ndlovu Care Group (NCG)

Listing 16.2.5.4
Ring Insertion/ Removal
Safety Population

Centre Participant ID	Visit Returned	Return Date	Package Opened	Return			Comments
				Appearance of Returned Ring	Color of Returned Ring	Other Comments on Appearance of Ring	
Centre XX XXXXXXX	Screening / Enrollment / Trial Month XX / Trial Month XX (Unscheduled X) / Exit visit	ddMMMyyyy	Yes / No	Appears used: XXXXXX / Appears not used: XXXX / Not sure: XXXXXXX	White to off-white cream-colored / Slight yellow to yellow / Tan / Brown / Other color: XXXXXX		

Duration = (Removal Date – Inserted Date)+1

Centre 01: Madibeng Centre for Research (MCR); Centre 02: MatCH Research Unit (MRU); Centre 04: Qhakaza Mbokodo (QM);

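### SAP 9.4.4 divides self-reported days of wear by a fixed 30 days, leaves the unit (visit or ring) unsettled between text and shells, and misclassifies wear on either reading

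*SAP*

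**What the plan says.** Under its methods for self-reported adherence, SAP 9.4.4 states: "Self-reported adherence to the ring regimen will be calculated per visit". The rate is 100 times days worn over days expected. The numerator uses ring insertion/removal log and expulsion/removal log data recorded "at the scheduled visit and any preceding unscheduled visit between the current and the previous scheduled visit". For the denominator, the total number of days that the participant was "expected to wear the ring is a calendar month (30 days) from the insertion date". Results fall into three categories: at least 90%, 80% to below 90%, and below 80%. The section gives no multiplier for the number of rings, no adjustment for actual visit dates and no cap.

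The shells are organised differently. Table 14.3.5.5 has rows by month of ring use. Listing 16.2.5.2 has one insertion date, one removal date, one duration and one scheduled duration per row. Its footnotes attribute days out to a particular ring and treat missing or partial insertion and removal dates as missing data. Table 14.3.5.5 takes percentages over participants with available data.

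On timing, Protocol 5.13 says that during 3-monthly follow-up "the participants should self-insert one ring during the trial visit and each of the two additional rings at monthly intervals". SAP 6.6 gives each scheduled visit a window of plus or minus 7 days, and SAP 9.2 describes the period a ring is to stay in place as 30 days plus or minus 7. The footnote to Listing 16.2.5.4 defines "Duration of Ring Use = (Removal Date – Inserted Date)+1".

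**The concern.** An adherence rate should be the share of expected days on which a ring was worn, so numerator and denominator must cover the same period. Here the numerator follows the interval between scheduled visits, or the time a ring was actually kept, while the denominator stays at 30 days. Once women move to 3-monthly visits, one visit covers three rings. Even for a single ring, the visit window lets the actual period run shorter or longer than 30 days.

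Self-reported pattern of ring use is a stated exploratory endpoint, and SAP 7.3 names self-report as a subjective adherence measure. Table 14.3.5.5 presents the rate in three bands, so errors around 80% to 90% move women between bands. Because the text says per visit and the shells are per ring, two programmers could also produce different tables from the same data.

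**Working it through.** The plan states no numerical result for this endpoint, so there is no figure to reproduce. The check applies the rule as written.

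**Inputs**
- Denominator: 30 days (SAP 9.4.4).
- Three rings per 3-monthly interval (Protocol 5.13), taken as about 91 days.
- Visit window: plus or minus 7 days (SAP 6.6).
- Day count: removal minus insertion plus 1 (Listing 16.2.5.4). That this also applies to the duration in Listing 16.2.5.2 is an assumption, so both counts are shown below.

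**Reading A: one rate per visit, as in the text.** Rate = 100 × days worn ÷ 30.
- Full use over 91 days: 91/30 = 303%. Seen 7 days early: 84/30 = 280%.
- 27 days worn out of 91: 27/30 = 90%, the top category. The actual share is 27/91 = 29.7%.

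**Reading B: one rate per ring, as in the shells.** Rate = 100 × (days in place − days out) ÷ 30.

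Uninterrupted wear with early removal:

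| Removed on day | With +1 | Without +1 |
|---|---|---|
| 23 | 24/30 = 80.0% | 23/30 = 76.7% |
| 24 | 25/30 = 83.3% | 24/30 = 80.0% |
| 25 | 26/30 = 86.7% | 25/30 = 83.3% |
| 26 | 27/30 = 90.0% | 26/30 = 86.7% |

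Days 23 to 25 lie inside 30 ± 7, yet none reaches 90% on either count.

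Late removal with interruption, ring kept 37 days with 11 days out: (37 + 1 − 11)/30 = 27/30 = 90%. The actual share is 27/38 = 71%.

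Twenty-seven days of wear across a 3-monthly interval: 9 days on each ring gives 9/30 = 30% three times, correctly below 80%. All 27 days on one ring gives 90% for that ring. The two rings never inserted have no dates, so they may drop out as missing instead of scoring 0%.

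**With expected days matched to elapsed days:** 27 of 91 gives 29.7%; uninterrupted wear to day 23 gives 100%; the interrupted 37-day ring gives 71%.

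**The case against.** The strongest reply is that the denominator wording is singular (one ring, one insertion date), that both shells are per ring, and that the per-visit reading is therefore not what would be programmed. Women are told to keep each ring in for one month, so 30 days is the prescribed regimen and a defensible denominator. During 3-monthly follow-up, two of every three ring changes happen at home and are not tied to the clinic window. The bands are not the only display either: expulsions and removals have their own table (14.3.5.7), the questionnaires tabulate removals and reasons, Listing 16.2.5.2 prints each duration and rate, and Table 14.3.5.3 shows replacement intervals. No test or decision uses this rate.

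Much of this stands. It makes the per-ring reading plausible and limits the consequences. It does not remove the conflict between text and shells. Nor does it rescue the fixed 30 days: the numerator is not confined to the first 30 days after insertion, so wear after day 30 offsets days out before it. At an early in-window visit the woman is instructed to remove the ring, so the remaining days were not hers to wear it.

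**Conclusion.** The rule is wrong as written. On the per-visit reading it can exceed 300% and put 27 days of wear in 91 into the top category. On the per-ring reading it scores uninterrupted in-window wear to day 23, 24 or 25 at 80% to 87%, and 71% wear over 37 days at 90%. The per-ring figures assume the +1 convention; dropping it lowers the early-removal scores further.

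Four stronger conclusions might be inferred, and the documents do not support them:
- That 27 of 91 days always scores 90%, or that nearly all women reach the top band once 3-monthly visits begin. Both need the per-visit reading, which the shells contradict.
- That one reading produces both errors at the same visit. Per visit, full use seen 7 days early at a 3-monthly visit scores 280%; the penalty for early removal arises at monthly visits or for single rings.
- That a known proportion of ring-months is misclassified. The documents give no distribution of visit timing. The exact early-day cut-off also moves with month length: 5 days early in a 31-day month is day 26, exactly 90% with +1.
- That the three bands are the only report of self-reported use.

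Impact is limited. This is one descriptive summary within an exploratory endpoint. Primary adherence rests on ring residual levels (SAP 9.2), and the per-protocol exclusions in SAP 7.2 do not name this rate.

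**What to change.** State one unit in SAP 9.4.4 and align Table 14.3.5.5 and Listing 16.2.5.2 with it. For each interval between scheduled visits:
- **Expected days:** actual days from the previous scheduled visit (or enrolment insertion) to the current visit or last product use visit, minus documented product holds.
- **Worn days:** sum over rings of days in place minus days out, with dispensed rings never inserted counted as zero days worn. Use the same day-count convention as for expected days, so that a change day is not counted twice.
- **Cap:** 100%.

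Report late replacement separately, using the interval categories of Table 14.3.5.3 (below 23, 23–37, above 37–84, above 84 days). This is needed because one ring kept for a whole 91-day interval would still score 91/91 = 100% despite two missed replacements. Dividing by each ring's own insertion-to-replacement interval would have the same fault.

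The cost is a short text change, two revised shells and one reprogrammed derivation. No new data are needed: dates come from the ring log, the expulsion log and, for interruptions due to adverse events, the AE form. Rates in the 3-monthly phase may look less favourable.
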